HRPO Protocol

1) Protocol Title (Version # and/or Version Date)

The Emotions and Decisions of Couples, #12-433, v. 06/13/2018

2) IRB Review History

N/A

3) Objectives

The proposed study is an experimental comparison of the effects of alcohol on arousal and emotion-regulation between 112 Distressed Violent (DV) and 112 Distressed Nonviolent (DNV) partners. One partner from each DV couple will be pseudo-randomly selected and yoked to a DNV partner of the same sex and a relationship satisfaction within a five-point range for participation in the experiment. To test the overall hypothesis that over-arousal is a mechanism through which alcohol is associated with increases in the frequency and severity of IPV, the selected partners will participate in a counter-balanced placebo session and alcohol administration session during which EEG, psychophysiology and pupillary response measurements of arousal will be collected during an emotion regulation task.

Specific Aim 1: To determine if normal increases in arousal after alcohol exposure is potentiated by evocative partner stimuli is greater for distressed violent (DV) partners compared to distressed nonviolent (DNV) partners. *Hypothesis 1a:* DV and DNV partners will experience comparable alcohol related increases in arousal. *Hypothesis 1b:* DV partners will demonstrate greater arousal increases by evocative partner displays than DNV partners. *Hypothesis 1c:* DV partners will experience greater arousal when exposed to alcohol and evocative partner stimuli than DNV partners.

Specific Aim 2: To determine if alcohol induced arousal interferes with DV partners' ability to regulate emotion in response to evocative partner stimuli compared to DNV partners. *Hypothesis 2a:* Emotion regulation during evocative stimuli will be reduced compared to neutral stimuli. *Hypothesis 2b:* Emotion regulation during evocative stimuli will be reduced by alcohol. *Hypothesis 2c:* DV partners will be less able to regulate emotion during evocative stimuli than DNV partners. *Hypothesis 2d:* Alcohol will interfere with DV partners' ability to regulate emotion during evocative stimuli compared to DNV partners.

4) Background

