Experimental administration of low to moderate alcohol (BAC up to .09g%) has also been shown to produce increases in pulse rates and finger pulse volumes, faster heart rate (HR), lower interbeat interval (i.e., lower heart rate variability), and higher skin conductance level (Burish, Maisto, & Shirley, 1982; Levenson, Sher, Grossman, Newman & Newlin, 1980). As with EEG, all of these psychophysiological changes with alcohol exposure are consistent with a physiologically aroused state (Burish, Maisto, & Shirley, 1982; Levenson, Sher, Grossman, Newman & Newlin, 1980). Similar to experimental studies of arousal and aggression, experimental studies of the conditions under which alcohol is related to aggression also find that alcohol is associated with aggressive behavior only under conditions of provocation and frustration (see Exum, 2006 for review). Furthermore, experimental manipulation of alcohol limb effects (i.e. ascending vs. descending limb) have provided evidence of increased aggressive tendencies on the ascending limb compared to the descending limb, thus providing further evidence of the role of alcohol induced arousal playing a potential role in IPV (Giancola & Zeichner, 1997).

In summary, the current application is investigating over-arousal as a mechanism through which alcohol is related to the increase in the frequency and severity of IPV. The experimental literature would suggest that the cortically and psychophysiological arousing effects of alcohol during the ascending limb of intoxication and at peak BAC are compounded by the arousal created by DV couples' distinct conflict patterns leading to an increase in IPV. In addition, the literature suggests that DV couples' have difficulty regulating emotion in highly aroused states, and may be even less able to do so after alcohol use. This research will be used to inform the development novel interventions for IPV where, currently, no effective interventions exist.

5) Inclusion and Exclusion Criteria

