EEG, Psychophysiology and Pupillary Response Acquisition - EEG and psychophysiology data will be collected using the BrainVision actiCHamp 64-channel, DC amplifier, 24-bit resolution, biopotential system. EEG data will be recorded with filters set at 1 and 30Hz, digitized at a sampling rate of 512Hz and stored on a computer using the PyCorder software. EEG data will be recorded to collect a 5-minute baseline measurement prior to administration of alcohol or placebo beverage. After beverage administration data will be collected for the duration of the emotion-regulation task (see below). To reduce confounding results due to artifacts, EEG signals will be examined for contamination by muscle activity and eye movement. Fast Fourier Transformation (FFT) analysis will be applied to 6-10 second epoch samples (corresponding to the delivery of stimuli) allowing for 1-s pre- and post-stimuli artifact subtraction with the spectral graph ranging from 0 to 30Hz at 0.5Hz-resolution. FFTs will be performed using EEGLab software to calculate 1) Absolute power (AP; power density of each frequency band expressed in microvolts squared; mV^2/Hz); 2) Relative power (RP; proportional contribution of each band to the total power across 1 – 30Hz). AP and RP will be transformed into Fisher's z-scores for statistical analyses. Skin conductance (SC) will be collected using the BrainVision GSR module with leads placed on the left index finger and left middle finger. SC will be recorded to collect a 5-minute baseline (as with EEG) measurement and for the duration of the emotion-regulation task and time-locked to evocative stimuli. SC data will be subjected to detrending and transformed to Fisher's z-scores for statistical analysis. Respiration and HRV will be measured using an integrated BrainVision respiration belt, and an EKG in Lead II position. As with EEG, baseline measures will be collected, and time locked to evocative events. EKG data will be quantified as respiratory sinus arrhythmia (RSA) which is a unique measure of parasympathetic activity and self-regulatory ability. Respiration and HRV data will also be transformed to Fisher's z-scores for statistical analysis. Pupillary response data will be collected using the EyeLink 1000 system high speed camera by SR Research (see sample data). Corneal reflection will be recorded at 250 Hz. The left and right pupil diameter measures will be averaged offline and baseline measures (1 sec prior to trial onset) will be subtracted. The difference between the maximum diameter during the trial and the baseline diameter will be calculated and transformed to Fisher's z-scores for statistical analysis. E-prime will control the flow of the emotion regulation task and generate timestamps to denote conditions for which all biopotential data can be analyzed.

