Specific Aim 1: To determine if normal increases in arousal after alcohol exposure is potentiated by evocative partner stimuli and is greater for DV partners compared to DNV partners. We will conduct a 2 (beverage condition: alcohol vs. placebo) x 2 (stimulus: evocative vs. neutral) repeated measures ANOVA with a between-subjects factor (partner type: DV vs. DNV). To test whether alcohol increases overall arousal (**Hypothesis 1a**), we will examine the main effect of alcohol vs. placebo on arousal variables, collapsing across partners and stimuli during the WATCH condition as alcohol should effect the arousal of both partner types equally. To test whether DV partners are more aroused by evocative partner displays than DNV partners (**Hypothesis 1b**), we will test the interaction effect of partner type and stimulus type, collapsing across alcohol and placebo conditions. Finally, to test the hypothesis that alcohol induced increases in arousal above placebo will be greater for evocative than neutral stimuli (**Hypothesis 1c**) for DV vs. DNV partners, we will test the three-way interaction in the 2 (DV vs. DNV) x 2 (alcohol vs. placebo) x 2 (evocative vs. neutral) repeated measures ANOVA. Specifically, this contrast will examine the effect of partner type when comparing stimuli type (evocative) to beverage condition (alcohol) on arousal and provides a critical control given that conflict intensity may differ between DV and DNV couples. The 3-way interaction (Hyp1c) will allow us to be able to determine whether the change in arousal between alcohol and placebo sessions for the evocative stimuli differs between couple types. The arousal level of evocative stimuli is matched between alcohol and placebo sessions, thus allowing for a controlled examination of alcohol-induced increases in arousal for evocative stimuli across DV and DNV couples.

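### The planned pupil score cancels any sustained alcohol effect, so for pupil Hypothesis 1a tests only evoked dilation; unspecified detrending may do the same to skin conductance

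*Combined protocol and SAP*

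**What the plan says.** Section 3 (Objectives) states Hypothesis 1a as "DV and DNV partners will experience comparable alcohol related increases in arousal". In Section 14 (Data Management), the Data Analysis Plan for Specific Aim 1 makes this a question about overall arousal and says "we will examine the main effect of alcohol vs. placebo on arousal variables, collapsing across partners and stimuli during the WATCH condition". It does not say which variables are meant, or whether they are scored as level or as response to a clip.

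Section 4 (Background) grounds the expected alcohol effect in earlier findings of "faster heart rate (HR), lower interbeat interval (i.e., lower heart rate variability), and higher skin conductance level".

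The scoring is in Section 11 (Study Methods), under EEG, Psychophysiology and Pupillary Response Acquisition:

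- Pupil: "The left and right pupil diameter measures will be averaged offline and baseline measures (1 sec prior to trial onset) will be subtracted". The next sentence defines the variable: "The difference between the maximum diameter during the trial and the baseline diameter will be calculated and transformed to Fisher's z-scores for statistical analysis". No other pupil score is given.
- Skin conductance: "SC will be recorded to collect a 5-minute baseline (as with EEG) measurement and for the duration of the emotion-regulation task", time-locked to the evocative clips. Then: "SC data will be subjected to detrending and transformed to Fisher's z-scores for statistical analysis". The type and window of detrending are not stated, nor is the way the 5-minute baseline enters the score.
- EEG power, respiration and respiratory sinus arrhythmia (RSA): neither detrending nor a per-trial subtraction like the pupil's is described.

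**The concern.** A beverage main effect averaged over evocative and neutral clips is most naturally a question about state: is the person more aroused after alcohol than after placebo? Reactions to partner clips, and their modification by alcohol, are left to Hypotheses 1b and 1c. The plan nevertheless supplies one processed variable per measure for all three hypotheses. For pupil, that variable is a within-trial difference whose reference point is already under the influence of the drink. For skin conductance, the processing may or may not keep the level.

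Hypothesis 1a is the first link in the over-arousal mechanism that the study sets out to test. A flat pupil result, or disagreement between pupil and EEG, could be taken for physiology when it comes from the scoring. The predicted comparability of the two partner groups is also exposed: if distressed violent (DV) and distressed nonviolent (DNV) partners had different sustained pupil shifts, the planned score would show them as alike.

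**Working it through.** The plan gives no effect size, variance, alpha or power, so there is no stated figure to reproduce. The check is algebra, supported by simulations with assumed inputs.

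**Timing of the pupil baseline.** From the Emotion Regulation Task description, a trial takes 1 + 1.5 + 0.5 + 1.5 = 4.5 s before the clip, then 4 to 8 s of clip and 0 to 2.5 s of blank, so 8.5 to 15 s. There are 50 clips × 2 presentations = 100 trials: 100 × 8.5 / 60 = 14.2 min to 100 × 15 / 60 = 25.0 min. The upper end agrees with the stated duration of about 25 minutes. The task follows the beverage, so every 1-second baseline does too.

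**Pupil algebra.** Let T be the placebo level, P the evoked dilation, D a sustained alcohol shift and g an alcohol change in evoked dilation.

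Alcohol score − placebo score = [(T + D + P + g) − (T + D)] − [(T + P) − T] = g.

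D drops out whatever its size, and g is kept in full.

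**Pupil simulation.** Assumed: 224 people (112 + 112); 50 WATCH trials per session; paired test at two-sided 0.05; 300 runs per row. Assumed SDs are 1 between persons, 0.5 between sessions, 0.3 for trial-to-trial level, 0.2 for evoked response by person and session, and 0.1 (baseline) and 0.2 (maximum) for measurement. The undifferenced score is the mean trial maximum.

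| D | g | Planned score: estimate, rejected | Undifferenced: estimate, rejected |
|---|---|---|---|
| 0 | 0 | 0.001, 3.7% | 0.004, 3.0% |
| 0.5 | 0 | −0.002, 5.3% | 0.499, 100% |
| 1.0 | 0 | 0.001, 7.7% | 1.001, 100% |
| 0 | 0.1 | 0.103, 100% | 0.101, 50.3% |
| 0.5 | 0.1 | 0.102, 100% | 0.595, 100% |

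Because D cancels, the first three rows estimate the same rejection rate for the planned score: (11 + 16 + 23) / 900 = 5.6%, close to nominal. The fourth row shows that undifferenced diameter has its own cost. It carries the assumed between-session noise and detects a small evoked change less often.

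**Skin conductance.** Assumed: 5-minute baseline followed by a 25-minute task, a slow linear drift, and a step of 1.0 at the start of the task. Alcohol-minus-placebo difference in task mean:

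- Slope removed about the task mean: 6.526 − 5.527 = 1.0, kept in full.
- Linear detrend of the whole record: about 0.10. In closed form, the step starts at fraction a = 300/1800 = 1/6. Its fitted slope is [a(1 − a)/2] / (1/12) = 5/6. The task residual is 1/6 − (5/6)(1/12) = 7/72 = 0.097. The baseline residual is −35/72, so task minus baseline is 42/72 = 0.583 (simulated 0.59).
- Linear detrend of the task segment alone: 0.0, because the segment mean is set to zero in both sessions.

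**Hypotheses 1b and 1c.** For a constant shift c, evocative minus neutral is (E + c) − (N + c) = E − N. The shift cancels from both interactions however the measure is scored.

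**The case against.** The strongest reply is that Hypothesis 1a never says tonic. It speaks of arousal, and the analysis plan tests it during WATCH viewing. The Background's explicit level evidence concerns skin conductance; it lists no alcohol effect on resting pupil diameter. The protocol calls the measure a pupillary response, and Section 23 (Resources Available) supports it with dilation to salient stimuli. On that view a phasic pupil score is deliberate. This stands in part: the level reading of Hypothesis 1a for pupil is an inference from its being a main effect on overall arousal, collapsed over stimuli. It does not remove the mismatch, because the plan sends undifferentiated arousal variables to that test.

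Three stronger readings are tempting and not supported:

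- A reader might infer that these outcomes cannot show any alcohol effect. They can: a change in evoked response remains estimable, and the planned pupil score recovered an assumed change of 0.1 in every run.
- A reader might infer that skin conductance level is certainly detrended away. The documents leave the method open, and one ordinary reading loses none of the level shift. The pre-beverage baseline could also supply a reference, though its use is unstated.
- A reader might infer that Hypothesis 1a as a whole fails, or that a null pupil result would be taken to mean alcohol is not arousing. EEG power and RSA carry no such stated processing, and no rule reads the hypothesis from pupil or skin conductance alone.

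**Conclusion.** The point holds in a limited form. For pupil, a sustained alcohol shift of any size contributes exactly 0 to the planned score, so the Hypothesis 1a main effect tests only whether alcohol changes evoked dilation. That rests on the score as written, on trials being post-beverage, and on the shift adding equally to maximum and baseline. If a sustained shift also altered the evoked response, that part would appear as g.

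For skin conductance the finding is ambiguity: the expected level rise may be kept, partly lost or wholly lost (1.0, about 0.1 or 0.0 of an assumed 1.0). The sizes for whole-record detrending depend on the assumed step and record lengths; the range does not.

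Hypothesis 1a remains testable on EEG power and RSA, provided the Fisher's z step does not standardise within session. The text does not say, and such standardising would remove the session mean from every measure. The phasic scores suit Hypotheses 1b and 1c. This is worth settling before analysis; it does not affect the interaction tests.

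**What to change.** For Hypothesis 1a only, add one level score per measure from the signals already recorded:

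- Skin conductance: un-detrended level during WATCH trials, referenced to the 5-minute pre-beverage baseline.
- Pupil: undifferenced diameter, either the mean during WATCH clips or the pre-trial diameter averaged over all trials. The pre-trial second precedes the WATCH/DON'T REACT instruction, so it should not be presented as a WATCH measurement.

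Compare both within person between the alcohol and placebo sessions. State for each arousal variable whether Hypothesis 1a uses level or response. Keep the baseline-subtracted pupil score and the detrended skin conductance for Hypotheses 1b, 1c and Aim 2. State the detrending method and window, and what the z-transformation is. Do not standardise level scores within session.

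The cost is plan wording and one derived variable per measure, with no new data. The downside is that no pre-beverage pupil reference is described, so the pupil level contrast carries between-session variation and will be noisier than the phasic score.

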
Emotion Regulation Task - The proposed approach for studying emotion regulation has been used in several previous studies,⁶⁹ but we will utilize participant-tailored stimuli (video clips of partner's evocative behavior). During viewing, participants will be instructed to 1) experience the emotion they associate with the video (WATCH), or 2) to suppress the feeling of emotion (DON'T REACT). In the WATCH condition, participants will be instructed to let their

emotional experience occur naturally, and to pay attention to how they feel during the clip. In the DON'T REACT condition, participants will be instructed to attempt to suppress any feelings of emotion so as to prevent an observer watching physiological recordings from knowing that an emotional response has occurred. In both conditions, participants will be asked to indicate their corresponding emotional state using a slider (clicking and dragging with a mouse) on a continuous rating scale anchored by "very negative" (1) and "very positive" (100). A total of 50 unique video clips between 4 and 8 seconds in length will be used in the task; 25 evocative and 25 neutral. Each stimulus will be presented twice: once in the WATCH condition and once in the DON'T REACT condition. On each trial, participants will view a blank screen (1 second), fixation cross (1.5 sec), blank screen (.5 sec), the instruction (WATCH or DON'T REACT; 1.5 sec), the video clip (4-8 sec), and a blank screen (up to 2.5 seconds). The total amount of time required for the task will be approximately 25 minutes. Ratings obtained during the emotion regulation task will be averaged across stimulus type and regulation condition for the placebo and alcohol sessions for statistical analysis.

Participant Remuneration: Each participant will be paid \$20 per hour for their participation in the study. Each partner will have the opportunity to earn \$40 for his/her participation in the *Stimuli Acquisition Session* (\$80 total). The partner invited back for the *Emotion-Regulation Sessions* will have the opportunity to earn \$100 for his/her participation in the *Alcohol beverage Emotion-Regulation Session* and \$20 in the *Placebo beverage Emotion-Regulation Sessions* for a total of \$200 per couple. Participants will receive remuneration in the form of Visa or similar gift cards.

12) List of Appendices

Scale Purpose	Scale Name	Use/Source	α	Population

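### The pupil score searches the whole trial for its maximum and takes its baseline before the trial, so pre-clip dilation and carry-over can dilute the evocative-neutral contrasts on that measure

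*Combined protocol and SAP*

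**What the plan says.** Section 11, in the paragraph on EEG, psychophysiology and pupillary response acquisition, averages the left and right pupil diameters and says that "baseline measures (1 sec prior to trial onset) will be subtracted". The score follows: "The difference between the maximum diameter during the trial and the baseline diameter will be calculated". It is then standardised for analysis.

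The Emotion Regulation Task paragraph of the same section, repeated in section 12 under Experimental Tasks, sets out the trial. First "participants will view a blank screen (1 second), fixation cross (1.5 sec), blank screen (.5 sec"), then "the instruction (WATCH or DON'T REACT; 1.5 sec"), then "the video clip (4-8 sec), and a blank screen (up to 2.5 seconds").

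No inter-trial interval, trial order or clip-only pupil window is stated. The companion measures are tied more closely to the stimulus: the EEG epochs of 6-10 s equal the clip plus 1 s on each side, skin conductance is time-locked to evocative stimuli, and respiration and heart-rate variability to evocative events.

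Section 14 (Data Analysis Plan, Specific Aim 1) tests partner type by stimulus for Hypothesis 1b, and partner type by beverage by stimulus for Hypothesis 1c, on the arousal variables. Pupil response is one of these, and none is named as primary.

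**The concern.** Both hypotheses need a score that reflects the response to the clip. Three features of the stated rule work against that.

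- **Search window.** It opens 4.5 s before the clip and contains the instruction screen. Dilation from preparing to suppress or to watch, or a chance peak before the clip, can set the maximum. Such a trial says little about the clip.
- **Baseline.** With no gap between trials, the second before trial onset lies in the previous trial's closing blank, and overlaps the previous clip if that blank lasts under 1 s. Any remaining response to the previous clip is then subtracted from the current score. If trial order is random this mainly adds noise. If trials are blocked by stimulus type it pulls the evocative-neutral contrast towards zero, because evocative trials are mostly preceded by evocative ones.
- **Window length.** A maximum tends to grow with the time searched. Clips run from 4 to 8 s, and nothing says that length is matched between evocative and neutral clips.

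At stake is sensitivity for Hypotheses 1b and 1c on pupil response. EEG, skin conductance, respiration and heart-rate variability are untouched.

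**Working it through.** **1. Reproduce the plan's timing.** The plan gives no power calculation; its only figure that depends on trial timing is the task length: "The total amount of time required for the task will be approximately 25 minutes".

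- Clips: "A total of 50 unique video clips between 4 and 8 seconds in length will be used in the task; 25 evocative and 25 neutral". Presentations: "Each stimulus will be presented twice: once in the WATCH condition and once in the DON'T REACT condition". Trials per session = 50 x 2 = 100.
- Pre-clip time = 1 + 1.5 + 0.5 + 1.5 = 4.5 s.
- Upper limits: 4.5 + 8 + 2.5 = 15 s; 100 x 15 = 1,500 s = 25.0 min.
- 6 s clip, full blank: 13 s; 100 x 13 = 1,300 s = 21.7 min.
- Lower limits: 4.5 + 4 + 0 = 8.5 s; 100 x 8.5 = 850 s = 14.2 min.

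The 25 minutes reproduces exactly at the upper limits, where no time is left for a gap between trials. With 6 s clips about 200 s remain, or 2 s per trial, so a gap is possible though none is stated.

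**2. Share of the search window that is clip** = clip / (4.5 + clip + closing blank).

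| Clip | Closing blank 0 s | Closing blank 2.5 s |
|---|---|---|
| 4 s | 4/8.5 = 47% | 4/11 = 36% |
| 6 s | 6/10.5 = 57% | 6/13 = 46% |
| 8 s | 8/12.5 = 64% | 8/15 = 53% |

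The pre-clip screens take 4.5/15 = 30% to 4.5/8.5 = 53%.

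**3. Distance of the baseline from the previous clip**, with no gap and a closing blank of b seconds. The planned baseline covers b - 1 to b seconds after that clip ends: 1.5-2.5 s for b = 2.5, and inside the clip for b below 1. The 0.5 s blank before the instruction runs from 2.5 to 3.0 s into the trial, so it covers b + 2.5 to b + 3.0 s: 5.0-5.5 s for b = 2.5, and 2.5-3.0 s for b = 0.

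**4. Illustrative simulation.** The documents contain no pupil data, so every input here is assumed:

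- true evocative-neutral difference 0.1 mm; neutral clip response 0.1 or 0.2 mm;
- instruction response 0, 0.15 or 0.3 mm;
- noise SD 0.1-0.2 mm with time constant 1.5-4 s;
- clip length uniform on 4-8 s, closing blank 2.5 s, no gap;
- 25 evocative and 25 neutral trials, 300 simulated people per scenario.

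The comparison score is the maximum from clip onset to 1 s after the clip, minus the mean of the last second before the instruction.

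| | Random order | Blocked by type |
|---|---|---|
| True difference recovered, planned score | 31-90% | 7-64% |
| True difference recovered, clip-locked score | 63-97% | 61-89% |
| Signal-to-noise ratio, planned / clip-locked | 0.49-1.00 | 0.11-0.75 |

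The maximum fell before clip onset in 2-58% of trials, depending mainly on the instruction response relative to the clip response. In no scenario did the planned score recover more of the difference than the clip-locked maximum. Simulation error on the ratios is several percent. People did not differ in their true effect, so these losses are upper-end for a group interaction.

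**5. Scale.** With 112 per group (assumed: two-sided 0.05, 80% power), the detectable standardised difference is (1.96 + 0.84) x sqrt(2/112) = 0.374. Were a contrast of that size attenuated to 90%, 70% or 50%, power would be 71%, 50% or 29%. These figures translate a given attenuation; they do not predict it.

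**The case against.** The strongest reply is that the rule is only loosely worded. Because EEG is cut around the clip and other signals are time-locked, trial may mean the clip presentation. The window shares and the previous-trial baseline would then fall away, and the baseline second would sit on the instruction screen. A baseline shift between WATCH and DON'T REACT would largely cancel from evocative minus neutral, since every clip appears once under each instruction. This reading is possible, but the task description lists the blank, fixation and instruction screens as parts of each trial, so the literal reading is the natural one. The text should settle it.

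Several limits on size also stand:

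- A share of time is not a share of a maximum. With a neutral response of 0.2 mm, no instruction response and low noise, only 2% of maxima fell before the clip and recovery was 90% against 93%.
- The closing blank can hold a slow but genuine clip response. Clip plus full closing blank is 6.5/11 = 59% to 10.5/15 = 70% of the trial.
- An unstated inter-trial interval would weaken the carry-over argument.
- Averaging 25 trials per cell, with an assumed between-person SD of 0.10 mm in the true effect, narrows the gap. With a 6 s clip, an instruction response of 0.08 mm, noise SD 0.10 mm and random order, the within-person standardised difference was 0.92-0.93 for the planned score and 0.94 for a fixed clip window.
- Clip length would bias the group contrast in Hypothesis 1b only if it differed by stimulus type and by group. Nothing in the documents suggests that.

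A reader might go further and infer that a brighter video constricts the pupil and pushes most maxima off the clip. The documents give no screen or clip brightness, and both clip types come from the same filmed discussion, so that inference is unsupported.

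**Conclusion.** The point holds as a weakness in a stated scoring rule. Taken literally, between 36% and 64% of the searched window is clip, the instruction lies inside the window, and the baseline precedes the trial. The pupil score can therefore carry pre-clip and instruction-related dilation and, if there is no gap between trials, the previous clip's response. The direction is towards a weaker evocative-neutral contrast for Hypotheses 1b and 1c.

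The size is open. Under the assumptions shown, the loss in signal-to-noise ratio runs from negligible to about half in random order and is larger if trials are blocked; real differences between people would reduce it for the group interactions. The conclusion rests on the literal meaning of trial and, for the carry-over part, on the absence of an inter-trial interval.

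It would be tempting to conclude that much of the pupil score is not a clip response and that the contrasts are materially diluted. The documents show only that this can happen. The matter is a worthwhile, inexpensive improvement to one of several arousal measures.

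**What to change.** Before any results are seen, amend the pupil paragraph in section 11 to:

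1. define trial onset, and state the trial order and any inter-trial interval;
2. score the pupil in a fixed-length window after clip onset that every clip contains, so within the first 4 s, located by the existing E-prime time stamps; clip length then cannot affect the score;
3. subtract a baseline from the 0.5 s blank just before the instruction in the same trial (at 250 Hz, 0.5 x 250 = 125 samples);
4. keep the whole-trial maximum as a secondary score.

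The cost is protocol wording and a scoring script. The recordings need no change, and the new score enters the planned repeated-measures ANOVA as it stands. The downside is that late responses to the longest clips are left out of the main score; the secondary score still covers them.
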